- Any other Grade 4 toxicity or unmanageable Grade 3 toxicity.

Occurrence	Action
1st - 2nd	Hold ACP-196 until recovery to Grade ≤ 1 or baseline; may restart at original dose level
3rd	Hold ACP-196 until recovery to Grade ≤ 1 or baseline; restart at 100 mg once daily
4th	Discontinue ACP-196

Subjects in Cohort 1 (ACP-196 monotherapy) who do not experience at least an minimal response (MR) after 2 cycles of study treatment may have dexamethasone (40 mg once weekly) added to their treatment.

Whenever possible, any dose adjustment of ACP-196, including adding dexamethasone to subjects in Cohort 1, should be discussed between the investigator and the Acerta Pharma medical monitor before implementation. The appropriate clinic staff should dispense the study drug for the new dose level and instruct the subject/caregiver about the change in dose level. Any changes to the dosing regimen must be recorded in the appropriate eCRF.

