5.5 ENDPOINT DATA ANALYSIS

5.5.1 Safety Endpoint

Safety summaries will include summaries in the form of tables and listings. The frequency (number and percentage) of treatment emergent AEs will be reported in each treatment group by MedDRA System Organ Class and Preferred Term. Summaries will also be presented by the severity of the adverse event (per CTCAE, v4.03) and by relationship to study drug.

Laboratory shift tables containing counts and percentages will be prepared by treatment assignment, laboratory parameter, and time. Summary tables will be prepared for each laboratory parameter. Figures of changes in laboratory parameters over time will be generated.

Results of vital sign assessments and physical exams will be tabulated and summarized.

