## **10. STATISTICAL METHODS OF ANALYSIS**

## **10.1 General Principles**

Descriptive statistics will be used to summarize disposition, demographics, baseline characteristics, disease characteristics, prior anticancer therapy, concomitant medication, study drug administration, efficacy and safety outcomes. Descriptive summary of discrete data will be present the sample size and incidence as frequency and percentage. Descriptive summaries of continuous data will be present the sample size, group mean, standard deviation, median, and range.

Confidence intervals (CIs), when presented, will generally be constructed at the 95% level. For binomial variables, the exact method for CIs will be employed unless otherwise specified.

Calculation of time to event or duration of event (e.g., DOR) will be based on actual study day of event rather than nominal visit date.

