### 10.5.3 Exposure to Study Drugs

Separate analysis will be performed for acalabrutinib and dexamethasone. Descriptive statistics (n, mean, standard deviation, median, minimum and maximum values) will be used to summarize:

- Duration of exposure (the interval between first dose date and last dose date)
- Actual cumulative dose administered
- Average dose (the ratio of actual cumulative dose administered and Duration of exposure): daily dose for acalabrutinib and weekly dose for dexamethasone
- Relative dose intensities (the percentage of actual cumulative dose to the planned cumulative dose)

The reasons for acalabrutinib dose withholding and reduction will be summarized and presented as the number and percentage of subjects with non-missing data per category.

- Dose withholding of acalabrutinib is defined as missing dose for  $\geq 7$  consecutive days.
- Dose reduction defined as taking lower dose level (100 mg per day) for acalabrutinib for  $\geq 3$  consecutive days.

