### 10.6 Analyses of Safety Endpoints

Safety analyses will be performed on All-treated population by treatment cohort.

Analyses of adverse events (AEs) will be performed on treatment-emergent AE (TEAE) data, unless otherwise specified. TEAEs are defined as those events with onset or

worsen date on or after the date of first dose of acalabrutinib, through the treatment phase to last dose of acalabrutinib, and within 30 days following the last dose of acalabrutinib, whichever is later. Common Terminology Criteria for Adverse Events (CTCAE) Version 4.03 or higher is used for AE grading.

Treatment-emergent AEs will be summarized in 3 groups: (1) acalabrutinib monotherapy, (2) acalabrutinib + dexamethasone, and (3) crossover from monotherapy to acalabrutinib + dexamethasone therapy. By this grouping method, AEs among subjects assigned to acalabrutinib monotherapy will be reported in group 1 when AEs occurred before crossover, and AEs occurred on/after crossover will be reported in group 3. Treatment-emergent AEs occurred on or after crossover will be summarized in the crossover group. Treatment-emergent AEs occurred before crossover will be summarized in the monotherapy group. All AE terms will be coded by Medical Dictionary for Regulatory Activities (MedDRA) Version 19.1 and will be presented by system organ class (SOC) and preferred term (PT). Treatment-emergent AEs will be summarized by SOC and PT and by CTCAE toxicity grade. The drug-related AEs, serious adverse events (SAEs) and drug-related SAEs, AEs leading to treatment discontinuation, dose delay and dose modification will be summarized by PT by CTCAE toxicity grade.

Death will be reported in a listing and summarized. A table will be provided for grade 5 AE and the relationship with any study drug.

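### The three-group adverse-event percentages ignore time at risk, so monotherapy can look safer when its pre-crossover window is shorter than the combination's

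*SAP*

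**What the plan says.** SAP section 10.6 sets the reporting groups: "Treatment-emergent AEs will be summarized in 3 groups: (1) acalabrutinib monotherapy, (2) acalabrutinib + dexamethasone, and (3) crossover from monotherapy" to combination therapy. It then applies a cut to one randomised cohort only: "AEs among subjects assigned to acalabrutinib monotherapy will be reported in group 1 when AEs occurred before crossover", with anything on or after crossover moved to group 3. Nothing comparable applies to Cohort 2, whose treatment-emergent window extends to events "within 30 days following the last dose of acalabrutinib, whichever is later".

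The summary measure is a crude proportion. SAP section 10.1 says: "Descriptive summary of discrete data will be present the sample size and incidence as frequency and percentage". Protocol section 5.5.1 says the same: the "frequency (number and percentage) of treatment emergent AEs will be reported in each treatment group". Neither document plans a person-time, exposure-adjusted or common-window summary of adverse events, and the SAP does not state the denominator for each of the three groups.

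SAP section 10.5.3 defines "Duration of exposure (the interval between first dose date and last dose date") and says "Separate analysis will be performed for acalabrutinib and dexamethasone". It does not mention the three groups or a split at crossover.

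There were three routes to added dexamethasone, all for Cohort 1 only:
- Protocol section 3.5.5.1: "Subjects in Cohort 1 (ACP-196 monotherapy) who do not experience at least an minimal response (MR) after 2 cycles of study treatment" may have it added.
- Protocol section 3.1: it can be added at documented progression.
- SAP section 3.1: a memo of 15 March 2016 stopped enrolment and let monotherapy subjects cross over. No minimum time on monotherapy is stated.

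**The concern.** The proportion of subjects with at least one event rises with the length of observation. Crossover shortens observation in group 1 and has no counterpart in group 2. If the pre-crossover window is the shorter one, group 1 will show a lower percentage than group 2 at the same underlying hazard, and a reader may credit the difference to the absence of dexamethasone.

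The primary objective is the safety profile with and without dexamethasone, and these are the tables that address it. The exposure summary as specified does not let a reader correct for the difference. A Cohort 1 subject's acalabrutinib duration includes time after crossover, when that subject's events are counted in group 3.

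**Working it through.** The documents state no figure for adverse-event observation time, so there is no stated figure to reproduce. The check is an illustration under equal hazards.

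**From the documents:** group 1 is cut at crossover; group 2 runs to treatment end plus 30 days; one cycle is 28 days; percentages are crude.

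**Assumed, because the documents do not give them:**
- a constant hazard h of first event, 0.05 to 0.20 per cycle, the same in both groups;
- crossover after M = 2 to 6 cycles;
- combination treatment for C = 4 to 12 cycles;
- every Cohort 1 subject crossing, except where stated.

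**Formulas:**
- Group 1 incidence = 1 − exp(−h × M)
- Group 2 incidence = 1 − exp(−h × (C + 30/28))

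Worked case, h = 0.10, M = 2, C = 6: group 1 is 1 − exp(−0.20) = 18.1%. Group 2 is 1 − exp(−0.10 × 7.07) = 50.7%.

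| h per cycle | M | C | Monotherapy | Combination | Gap (points) |
|---|---|---|---|---|---|
| 0.05 | 6 | 6 | 25.9% | 29.8% | 3.9 |
| 0.10 | 4 | 4 | 33.0% | 39.8% | 6.8 |
| 0.05 | 2 | 6 | 9.5% | 29.8% | 20.3 |
| 0.10 | 2 | 6 | 18.1% | 50.7% | 32.6 |
| 0.20 | 2 | 6 | 33.0% | 75.7% | 42.7 |
| 0.20 | 2 | 12 | 33.0% | 92.7% | 59.7 |

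In the first two rows the treatment periods are equal, so only the 30-day tail is lost.

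**Partial crossover.** If half of Cohort 1 crosses at 2 cycles and the rest are observed like the combination (h = 0.10, C = 6), monotherapy shows 0.5 × 18.1 + 0.5 × 50.7 = 34.4%, against 50.7%.

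**What matched person-time does.** Take h = 0.10 and count time up to the first event within each group's own window:
- Group 1 has 0.181 subjects with an event per subject. Expected time at risk is 0.181 / 0.10 = 1.81 cycles, and the rate is 0.181 / 1.81 = 0.10.
- Group 2 has 0.507 subjects with an event over 5.07 cycles, and the rate is again 0.10.

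The artefact disappears.

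**What unmatched exposure would do.** If a reader divided pre-crossover events by uncut acalabrutinib time, with crossover at cycle 2 of 6, the apparent rate would be 0.10 × 2 / 6 = 0.033 per cycle instead of 0.10. Exposure therefore has to be split at the same point as the events.

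**The case against.** The strongest case on the other side has five parts.

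**No comparison is designed.** Protocol section 5.2 says the study is not formally designed to compare the regimens, SAP section 5 tests no hypotheses, and number with percentage is the protocol's own summary. With at most 20 planned per cohort, a percentage near 33% has a 95% half-width of about 1.96 × √(0.33 × 0.67 / 20) = 0.21. This stands as a limit: the issue is interpretation, not an error rate. It does not remove the problem, because adjacent columns with no stated time at risk are what the reader is given.

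**Splitting at crossover is sound.** It keeps events under added dexamethasone out of the monotherapy column. Agreed; what is missing is the matching denominator.

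**The windows may be nearly equal.** Under Protocol section 3.8, definitive progression on the highest tolerable dose allowed leads to withdrawal from treatment. A Cohort 2 subject's window would then close soon after progression, and a Cohort 1 subject who crosses at progression loses mainly the 30-day tail. SAP sections 11 and 12 report very few responders, so short treatment in both cohorts is plausible. This also stands, and is why the lower end of the range is small.

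**A reader might infer that all the safety output favours monotherapy.** The documents do not support that. Events of clinical interest are tabulated by cohort (SAP 10.6.1). Laboratory, vital sign and ECOG windows (10.6.2 to 10.6.4) run to 30 days after the last acalabrutinib dose or the safety visit. Read literally, these keep post-crossover findings in Cohort 1, and any bias there can run the other way.

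**A reader might infer that 10.5.3 misstates exposure.** It does not. First-to-last-dose is a correct measure of acalabrutinib exposure, and the SAP plans no rate based on it. The 0.033 figure arises only if someone combines the two sections.

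**Conclusion.** The point holds for the three-group tables in SAP section 10.6. When pre-crossover time is shorter than combination time, monotherapy incidence is understated relative to the combination even with no added toxicity from dexamethasone. If combination subjects stopped sooner than monotherapy subjects crossed, the direction would reverse.

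The size cannot be fixed from the documents. Over the assumed scenarios with full crossover, the gap runs from about 4 points (6 cycles in each group, only the tail lost) to about 60 points (crossover at 2 cycles against 12 cycles of combination). It is smaller if few subjects cross. These figures rest on constant, equal hazards and assumed durations, and are not an estimate of what happened in this trial.

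It is also tempting to treat Cycles 1 and 2 as a window free of crossover. The documents do not support that either: crossover at progression or under the 2016 memo has no stated minimum time and can fall inside those cycles. The change is worth making because these tables serve the primary objective and the correction is cheap.

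**What to change.** **SAP 10.5.3.** Report the number of subjects at risk, and the duration and dose of each drug, for the same three groups as the adverse-event tables: Cohort 1 up to the day before first dexamethasone, Cohort 2, and Cohort 1 from first dexamethasone onwards.

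**SAP 10.6.** Keep the crude percentages and state each group's denominator. Beside them give exposure-adjusted incidence, defined as subjects with the event per patient-month at risk within that group's own window. Do this for all, grade 3 or higher, and serious treatment-emergent events.

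**SAP 10.6.1.** Tabulate events of clinical interest by the same three groups, with the same rates, so that they can be read alongside the main tables.

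**Optional.** If an early-window comparison over Cycles 1 and 2 is added, censor Cohort 1 subjects at crossover when they cross before the end of Cycle 2.

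The cost is some SAP wording and a few extra tables from event and dosing dates already collected. The exposure-adjusted rates assume a roughly constant hazard, so they supplement the percentages and do not replace them.

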#### **10.6.1 Adverse Events of Clinical Interest**

In addition to general analyses of adverse events, analyses will be conducted on selected AEs of clinical interest. The following are event of clinical interests (ECIs): cardiac events (including atrial fibrillation), anemia, cytopenias, hemorrhage including major hemorrhage, hepatic events, hypertension, infections, interstitial lung disease and pneumonitis, second primary malignancies, and tumor lysis syndrome. Details of ECIs is summarized in the Appendices of this SAP.

AEs of clinical interest are defined in [section 14.4](#) of the appendices.

Subject incidence rates of AEs of clinical interest will be tabulated by treatment cohorts and all-treated population.

### 10.6.2 Laboratory Abnormality

All of the laboratory tests are performed in central laboratory and/or in local laboratory. Analyses will be performed for laboratory test data collected at baseline and from first exposure to acalabrutinib to 30 days after last dose of acalabrutinib or up to the safety follow-up visit date, whichever is later. Laboratory test for hematology, serum chemistry, and T/B/NK cell count up will be performed in central laboratory with reference range and the results will be reported in standard international units or conventional units when appropriate. Applicable laboratory test results will be graded according to CTCAE Version 4.03 or higher. AMA (American Medical Association (AMA) Manual of Style 10th Edition 2017) laboratory values will be applied whenever reference ranges are not available (e.g., local laboratory data).

For selected laboratory test parameters, summary statistics (mean, standard deviation, median, minimum and maximum) will be produced at baseline, post-baseline values from the last visit, minimum and maximum post-baseline values, and changes of these post-baseline values from baseline. Post-baseline toxicity grade greater than baseline grade will be presented in the treatment-emergent laboratory abnormality table. Shift from baseline to the worst grade from first exposure to acalabrutinib to 30 days after last dose of acalabrutinib or up to the safety follow-up visit date, whichever is later, will be provided as shift tables for selected parameters.

To be included in the summary table, a subject must have at least one post-baseline value for the given time point.

- *Lymphocytosis*

Lymphocytosis is defined as an elevation in absolute lymphocyte count (ALC) of  $\geq 50\%$  compared to baseline and a post-baseline assessment  $>5 \times 10^9/L$  (Wang 2013). The number of subjects with at least one occurrence of lymphocytosis will be summarized. For subjects with lymphocytosis, resolution of lymphocytosis is defined as 1) a decrease of ALC value to the baseline level or lower, or 2) a decrease of ALC value that is below  $5 \times 10^9/L$ , whichever occurs first. Duration of lymphocytosis (DOL) is defined as the duration of time from the earliest date on which the ALC value met the lymphocytosis criteria at a post-baseline assessment to the earliest date on which a subsequent ALC value met the resolution criteria.

DOL = Earliest date of meeting resolution criteria -Earliest date of meeting lymphocytosis criteria + 1.

Subjects who developed lymphocytosis but whose lymphocytosis was not resolved prior to the analysis cutoff date will be censored at the last sample date with non-missing ALC value at or prior to the analysis cutoff date.

Summary statistics will be provided for time to lymphocytosis. KM estimates for DOL will be provided.

- *Hepatitis B Test*

Subjects with a history of hepatitis B virus (HBV) infection should be monitored monthly with a quantitative polymerase chain reaction (PCR) test for HBV DNA. Monthly monitoring should last until 12 months after last dose of acalabrutinib. Any subject with a rising viral load (above lower limit of detection) should discontinue study drug and have antiviral therapy instituted and a consultation with a physician with expertise in managing hepatitis B. A listing of subjects with any hepatitis B test will be provided.

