#### 10.6.3 **Vital Signs**

Analyses will be performed for vital sign safety data collected at baseline and from first exposure to acalabrutinib to 30 days after last dose of acalabrutinib or up to the safety follow-up visit date, whichever is later. Summary statistics (mean, standard deviation, median, minimum and maximum) will be produced for vital signs at baseline, post-baseline values from the last visit, minimum and maximum post-baseline values, and changes of these post-baseline values from baseline. In addition, blood pressure is graded and the maximum post-baseline grade will be presented. Systolic Blood Pressure is graded by CTCAE as Grade 0 ( $\leq 119$  mm Hg), Grade 1 (120-139 mm Hg), Grade 2 (140 – 159 mm Hg), Grade 3 ( $\geq 160$  mm Hg). Diastolic Blood Pressure is grade as Grade 0 ( $\leq 79$  mm Hg), Grade 1 (80 -89 mm Hg), Grade 2 (90 – 99 mm Hg), Grade 3 ( $\geq 100$  mm Hg). In order to be included in the table, a subject must have at least one post-baseline value for the given time point.

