#### 10.6.4 **ECOG Performance Score**

Change of ECOG score from baseline to the worst score during the period from first exposure to acalabrutinib to 30 days after last dose of acalabrutinib or up to the safety follow-up visit date, whichever is later will be provided as shift tables.

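### The SAP cuts adverse events at crossover but not laboratory, vital-sign or ECOG data, so values recorded after dexamethasone was added can appear under monotherapy

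*SAP*

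**What the plan says.** SAP 10.6 opens with a general rule: "Safety analyses will be performed on All-treated population by treatment cohort". SAP 6.2 defines the treatment cohorts as the two randomised arms and has no crossover cohort. Section 10.6 then makes one exception, for treatment-emergent adverse events: three groups, with a Cohort 1 subject's earlier events kept under monotherapy, while "AEs occurred on/after crossover will be reported in group 3".

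The later subsections do not mention crossover:

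- **Laboratory (10.6.2).** The data are "laboratory test data collected at baseline and from first exposure to acalabrutinib to 30 days after last dose of acalabrutinib"; a later safety follow-up visit extends the window. The summaries are "post-baseline values from the last visit, minimum and maximum post-baseline values" with their changes from baseline. The shift table is defined as "Shift from baseline to the worst grade from first exposure to acalabrutinib to 30 days after last dose of acalabrutinib", with the same extension.
- **Vital signs (10.6.3).** The data are "vital sign safety data collected at baseline and from first exposure to acalabrutinib to 30 days after last dose of acalabrutinib", with the same extension, and "blood pressure is graded and the maximum post-baseline grade will be presented".
- **ECOG (10.6.4).** The shift table shows "Change of ECOG score from baseline to the worst score during the period from first exposure to acalabrutinib" to the same end point.
- **Events of clinical interest (10.6.1).** Incidence is tabulated by treatment cohort and for all treated subjects. The crossover group is not named.

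Protocol 5.5.1 asks for laboratory shift tables by assigned treatment, and SAP 12 reports no major departure from the protocol's analyses.

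**The concern.** In Cohort 1, dexamethasone is added to continuing acalabrutinib. A window tied to acalabrutinib dosing therefore runs straight through crossover. The chosen summaries (last value, minimum and maximum, worst grade, maximum grade, worst score) are exactly the ones that a later treatment period can overwrite.

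The primary objective is the safety profile with and without dexamethasone. As written, one report would show a monotherapy column that stops at crossover for adverse events and one that continues past it for laboratory grades, blood pressure and ECOG. The dexamethasone label in Protocol Appendix 4 lists blood pressure elevation, hyperglycemia, potassium loss and liver enzyme elevation. Blood pressure grade is a named output of 10.6.3, and glucose, potassium, ALT and AST are in the chemistry panel of Protocol 4.1.12.

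Crossover is also not random. It was allowed at progression (Protocol 3.1), for less than a minimal response after 2 cycles (Protocol 3.5.5.1), or under the March 2016 memo, for which SAP 3.1 states no such condition. Later values may therefore also reflect disease course and longer follow-up.

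**Working it through.** The documents give no figure for this point and no count of subjects who crossed over. The check has a textual part and an illustrative part.

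**Which grouping applies**

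1. The default in SAP 10.6 is treatment cohort, and SAP 6.2 gives two of them.
2. The three-group exception is worded for adverse events only. Laboratory values, vital signs and ECOG scores are not adverse events.
3. Sections 10.6.2 to 10.6.4 name no grouping, crossover cut or new baseline, so the default applies. Protocol 5.5.1 points the same way for laboratory shift tables.
4. Events of clinical interest are adverse events, so either the three-group rule or the two-cohort definition could apply to 10.6.1. The SAP does not say which.

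**How much of one crossover subject's data falls after crossover**

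Post-baseline visits with chemistry, haematology and vital signs in Protocol Appendix 5:

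- Cycle 1, Days 8, 15, 22 and 28: 4
- Cycle 2, Days 15 and 28: 2
- Cycles 3 to 12, Day 28: 10
- Early termination/safety follow-up, counted once: 1
- Total: 4 + 2 + 10 + 1 = 17

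Crossover times and follow-up lengths below are assumed. The end of Cycle 2 is the earliest point under the minimal-response rule.

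| Crossover at end of | Followed to | Visits before | Visits after | Share after |
|---|---|---|---|---|
| Cycle 2 | Cycle 12 | 6 | 10 + 1 = 11 | 11/17 = 64.7% |
| Cycle 2 | Cycle 4 | 6 | 2 + 1 = 3 | 3/9 = 33.3% |
| Cycle 4 | Cycle 12 | 8 | 8 + 1 = 9 | 9/17 = 52.9% |
| Cycle 6 | Cycle 12 | 10 | 6 + 1 = 7 | 7/17 = 41.2% |

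In each case the last-visit value is a post-crossover value. The minimum, maximum and worst values may or may not be.

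**Effect on a table percentage**

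Each subject whose worst grade first occurs after crossover moves a Cohort 1 percentage by 100/n points: 100/20 = 5.0 at the planned n = 20, and 100/10 = 10.0 at n = 10 (assumed, because enrolment closed early).

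For a sense of range, let p be the share of Cohort 1 with the abnormality before crossover, f the share crossing over (taken as unrelated to p), and q the chance of a first abnormality after crossover. The rate shown under monotherapy becomes p + (1 − p) × f × q. All inputs are assumed.

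- p = 10%, f = 25%, q = 10%: 0.10 + 0.90 × 0.25 × 0.10 = 12.25%
- p = 10%, f = 75%, q = 30%: 0.10 + 0.90 × 0.75 × 0.30 = 30.25%
- p = 20%, same two settings: 22.0% and 38.0%

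**The case against.** The strongest reply is that two columns are inferred. The opening sentence of 10.6 covers adverse events too, and these are then shown in three groups, so the phrase does not settle the columns for the subsections. That is fair as far as it goes. But nothing extends the three groups beyond adverse events, and the SAP supplies neither a cut for non-AE values nor a crossover baseline. Even if three groups were intended, the tables could not be programmed from this text.

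A second reply is that Protocol 5.5.1 chose assigned treatment deliberately, and also asks for a breakdown by time and for figures over time. Those outputs would partly show when laboratory changes occurred. They do not cover blood pressure or ECOG, and the SAP's own shift table to the worst grade has no time dimension. Tabulating by assignment would still mix exposures.

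Third, the main safety tables are already split, and laboratory values that need treatment, discontinuation or dose modification are reported as adverse events under Protocol 6.1.1. This stands and narrows the problem. Laboratory grades below that threshold, blood pressure grades and ECOG scores remain unsplit.

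Fourth, the visit shares describe one hypothetical subject, and three of the four assume follow-up to Cycle 12, which may be optimistic for subjects who crossed over. This also stands. Counting early termination and safety follow-up as separate visits turns 3 of 9 into 4 of 10. Dropping the follow-up visit for a subject who moves to a long-term study turns 11 of 17 into 10 of 16. Neither changes the conclusion.

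Finally, the label adds that blood pressure effects are less likely with synthetic steroids except at large doses. The argument does not depend on that one effect.

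**Conclusion.** The concern holds. Following the SAP as written places post-crossover laboratory, vital-sign and ECOG values in the monotherapy column, which is inconsistent with its own handling of adverse events and with the primary objective. The last-visit laboratory or vital-sign value is post-crossover for every crossover subject assessed afterwards; extreme and worst values can be. The grouping of events of clinical interest is ambiguous rather than wrong.

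The size cannot be stated from the documents. It depends on how many subjects crossed over, when, and how long they were followed, and it is zero if none did. With cohorts of about 20 or fewer, a handful of subjects is enough to change a reported percentage visibly. The conclusion rests on reading the silent subsections under the default of 10.6 and the definition in 6.2. SAP 5 states that no formal hypotheses are tested, so the issue affects how the safety tables are read and not a test result. It should be fixed.

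**What to change.** State in SAP 10.6 that the three groups apply to 10.6.1 through 10.6.4, and add the following:

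- End monotherapy-group data at crossover, defined as the first dose of study dexamethasone added to the Cohort 1 regimen. Other corticosteroids, which exclusion criterion 9 (Protocol 3.4.2) allows during the study, should not trigger it.
- Give the crossover group's denominator: the subjects who crossed over.
- State the baseline for its changes and shifts: original baseline or last value before crossover.
- Add a table note that changes after crossover may be confounded with disease course and longer follow-up.
- Record in SAP 12 the departure from tabulating by assigned treatment.

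The cost is a few sentences and some extra table columns with small counts. No new data are needed: the adverse event split already requires the crossover date, and SAP 10.5.3 already uses first and last dexamethasone dose dates.
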